7.2.2 Additional Analysis Considerations

There are multiple subgroups of special interest in this cohort including individuals with therapy-related MDS and those with MDS/MPN overlap disorders. Each group may comprise up to 10% of the cohort. Individuals will be included/excluded from select substudies depending on the substudy focus. General questions from earlier discussions will be applicable to these individuals as attempts to elucidate the importance of genetic factors, quality of life changes and other issues are explored.

Along with selection and other biases that are applicable in cohort studies, the analysis of specific substudies will consider the impact of informative censoring. This is a potential issue in many studies of MDS patients since they are often elderly and have additional comorbidities. Note that many of the studies may have mortality endpoints and informative censoring for these can only occur when there are dropouts from mortality endpoint ascertainment. We expect that this loss to follow-up rate will be small which in itself limits the potential impact of informative censoring and, as always in studies performed under the auspices of the NCTN, we will work towards limiting this problem. The approaches to mitigating the impact of informative censoring will depend on the outcome of interest and the study design. At times, the endpoint can be redefined to lessen the risk of inferential error attributed to informative mortality censoring (e.g. use endpoint of time to progression or death rather than to progression). Consideration of competing risks and/or use of multistate models can be used and inference results examined in light of the simpler versus more complex model implications. In general stratifying by covariates correlated to the censoring factor can provide insight and in repeated measures analyses, stratification by missingness pattern can be useful in mitigating impact of informative censoring. The challenge is that it is not easy to examine the

randomness assumption required for unbiased inference. Strategies for exploring this issue typically involve introducing sensitivity analyses often after parameterizing a distributional shift (bias) that occurs when censoring is not random. These approaches often rely on the principal stratification framework applicable when evaluating causal estimands. This approach can be applicable if a continuous outcome measure is available in the responder subgroup.

Some of the study objectives require an analysis of longitudinal data with heterogeneity of personal trajectories. Analysis of repeated measurement data using growth curve models and estimation using the Generalized Estimating Equations (GEE) approach will likely be employed in some analyses. Health and Quality of Life (HQL) will be evaluated at each time point and summarized using simple descriptive statistics (e.g. mean, SD). When group differences are posited, models will be adjusted for baseline HQL. Partly conditional regression, conditioning on being alive at each time point, can be used to compare the longitudinal HQL measurements over time between the groups.¹¹⁰ Interactions with time will be tested for and if significant, group effects will be estimated separately for each time point. The missing data pattern of the HQL measurements will be examined using graphical techniques and logistic regression models conditional on survival. At each time point, estimates of the difference in HQL between the groups conditional on survival at that time point will be obtained using inverse probability of censoring weighted GEE with independent estimating equations¹¹¹ to account for missing data.

In response to the COVID-19 pandemic, the study is collecting data on the COVID-19 status (positive or negative), hospitalizations and medications received due to COVID-19. Also, the study is implementing a way to track protocol deviations associated with COVID-19. Several aims can be explored with the addition of the COVID-19-related data points. These may include evaluation the effect of COVID-19 on the study endpoints such as mortality, progression to AML, and hematopoietic stem cell transplantation.

Rev. Add7

Rev. 8/17 **8. The National MDS Study Pathology Review**

Diagnostic material from baseline must be submitted for review and classification by the study. Diagnostic material will be centrally reviewed at baseline for all enrolled cases and post-baseline for any cases where additional diagnostic bone marrow samples are collected.

The submitting pathologist and clinical research associate should refer to the MOP for additional guidelines.

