widely at diagnosis, although most cases have a tendency to exacerbate over time.² Previously considered a “pre-leukemic” syndrome, it is now understood that only about 30% of all MDS transform to acute myeloid leukemia (AML), the likelihood of transformation being significantly higher with increasing disease severity.^{2,13} In addition, the presence of rare variants such as the “overlapping” disorders that display features of both myelodysplasia and MPN, and the existence of hypoplastic (as opposed to the typical hypercellular) MDS pose difficulties in researching etiology and pathogenesis and developing appropriate therapies.^{14,15} The heterogeneity in MDS suggests the various subtypes may not represent a single disease entity. MDS constitute a spectrum of different progressive diseases with potentially different etiologies, some of which terminate in frank leukemia, while other, pathologically distinct variants may lead to progressive marrow failure.^{2,16,17} Related disorders such as ICUS and the recently reported clonal hematopoiesis of indeterminate potential (CHIP) present complex clinical conditions, the understanding of which could benefit from parallel studies of MDS.¹⁸

Treatments for MDS depend upon disease severity at diagnosis, and range from supportive care to hypomethylating agents (HMA), cytotoxic chemotherapy, and hematopoietic cell transplantation (HCT).¹⁹ HCT is the only available therapy with curative potential, although it is associated with substantial morbidity and risk of fatal complications, and may not be an appropriate therapy for all patients.²⁰ It is only considered in < 5% of MDS patients, and thus for approximately 95% of patients, therapeutic approaches are ultimately palliative.¹¹ Thus, more translational research is required to determine optimum strategies for distinct patient subgroups. The estimated 3-year survival of MDS patients relative to age-matched controls is 42%.²¹ As the incidence of MDS increases with age,⁹ and people live progressively longer lives, there is an urgency and necessity to better understand the natural history of MDS and identify new preventive and therapeutic interventions. Given the rarity and extensive heterogeneity of MDS, details of natural history can only be studied in the context of multi-center collaborations that facilitate close, protocol-specified longitudinal follow-up of a large patient cohort that is representative of the broad spectrum of the disease.

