- Locally or centrally detected genetic mutations meeting minimally acceptable criteria for allelic variant presence (ASXL1, ATRX, BCOR, BCORL1, BRAF, CALR, CBL, CEBPA, CSF3R, CUX1, DDX41, DNMT3A, ETNK1, ETV6, EZH2, FLT3, GATA2, GNAS, GNB1, IDH1, IDH2, JAK2, KIT, KMT21, KRAS, MPL, MYD88, NF1, NPM1, NRAS, PHF6, PPM1D,

Rev. 8/17

PRPF8, PTPN11, RAD21, RUNX1, SAMD9, SAMD9L, SBDS, SETBP1, SF3B1, SH2B3, SMC1A, SMC3, SRSF2, STAG2, STAT3, STAT5B, TET2, TP53, U2AF1, WT1, ZRSR2)

- No post baseline biological samples or data will be captured for those classified into the cross-sectional cohort .
- No post baseline biological samples or data will be collected from individuals who enroll and are classified as MDS, MDS/MPN overlap disorders, AML with < 30% blasts without core binding factor or acute promyelocytic leukemia, or ICUS after the relevant category-specific sample size limits have been reached.
- Sites will be notified by an email message, no later than the 12th month post-enrollment, when longitudinal follow-up is required. Individuals not assigned to the cross-sectional group by month 6 should submit specimens and data associated with the 6 month visit. The electronic case record for the individual will also be modified.
- Capture of biologic samples will be discontinued if the participant receives an HCT. Additional data may be collected from the CIBMTR on patients receiving a transplant.
- Biologic samples are submitted for cases in the longitudinal cohort at the time of AML diagnosis (i.e. blasts >30% and >=50% increase from baseline). Subsequent samples will not be collected for AML cases.
- Individuals may participate in other studies but will continue to submit data and specimens for this protocol.

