5.4.2 Assessment Schedule

QOL instruments will be administered at baseline, month 6, 1 year and yearly, thereafter, (see Table 4 in Section 6).

These patient-reported outcome assessment time points correspond to standard clinic office visits of routine care to minimize participant burden.

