5.5 Duration of Study

Patients will participate on this study unless:

- Hematopoietic cell transplantation occurs. Capture of biologic samples will be discontinued if the participant receives an HCT. Vital status follow-up will continue but other post-transplant data will be captured by the CIBMTR national registry.
- Extraordinary Medical Circumstances: If at any time the constraints of this protocol are detrimental to the patient's health, collection of additional data and samples should be discontinued. In this event submit data through Medidata Rave according to the schedule in the NHLBI-MDS Forms Completion Guidelines.
- Patient withdraws consent.

Rev. 1/17
8/17

6. Study Follow-Up Schedule

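### Section 7.2.2 targets QOL differences among everyone alive, but Section 5.5 implies no study QOL after transplant, so weighting cannot represent transplanted survivors

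*Protocol*

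**What the plan says.** **Target and estimator (Section 7.2.2).** The section first offers an option: "Partly conditional regression, conditioning on being alive at each time point" can be used to compare groups over time. It then commits: "estimates of the difference in HQL between the groups conditional on survival at that time point will be obtained". The method it names for this is weighting for missingness, "using inverse probability of censoring weighted GEE with independent estimating equations". The missing-data pattern "will be examined using graphical techniques and logistic regression models conditional on survival". Survival is the only conditioning event named. The section calls the outcome HQL; other sections call it QOL.

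**Follow-up after transplant (Section 5.5).** HCT is the first listed reason for participation to end. Biologic sampling stops, and "Vital status follow-up will continue but other post-transplant data will be captured by the CIBMTR national registry". Section 5.1 adds: "Additional data may be collected from the CIBMTR on patients receiving a transplant". That is a possibility, not a commitment, and QOL is not named.

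**QOL schedule (Section 5.4.2 and Table 4 in Section 6.1).** "QOL instruments will be administered at baseline, month 6, 1 year and yearly, thereafter". Neither place exempts transplanted participants. Section 5.2.2.1 lists both transplant status and QOL among the items recorded every 6 months.

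**The concern.** Censoring weights let observed participants stand in for similar participants who are not observed. This needs every member of the target population to have some chance of being observed. If QOL ends at HCT while vital status continues, a transplanted survivor is known to be alive, and so is in the target, but has no chance of contributing a QOL value. Section 7.2.2 does not name transplant as a cause of missing QOL.

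Two things are at stake. The first is labelling: a result reported as QOL among survivors would describe only the untransplanted, or a course as if transplant had not happened. The second is comparison. Section 1.2.7 says that higher-risk patients judged good candidates may be referred for HCT, so the unobserved share may differ between the groups being compared. Understanding QOL in relation to disease and treatment status is one of the aims in Section 2.

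**Working it through.** **1. Scale.** The protocol states no figure for this issue, so there is none to reproduce. Its only QOL sizing figure sets the scale. Section 7.2.1 gives 175 participants in two equal groups, a FACT-G difference of 5, a within-person SD of 10 and 90% power.

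- Per group: n = 2 × (1.960 + 1.282)² × 10² / 5² ≈ 84.1, rounded up to 85, so 170 in total against 175 stated.
- Power at 175 is 91.1% against 90% stated.

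The figure reproduces within 3%, so 5 points is a fair yardstick.

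**2. Can the weights work?** On the Section 5.5 reading, P(QOL observed | alive, transplanted) = 0.

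- If transplant status enters the weight model, the weight is 1/0 and undefined.
- If it is left out and weights are built from pre-transplant history, they are finite. The estimate then describes QOL as if no transplant had occurred, not QOL among those alive.

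**3. Size of the bias.** Let p be the transplanted share of survivors in a group, and d the post-transplant QOL shift not explained by earlier covariates. Against the alive-at-t target, the bias in the contrast has size |p₁d₁ − p₀d₀|.

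Inputs for p: <5% of MDS patients considered for HCT (Section 1.2.1, taken as 5%), and 11% transplanted in a patient survey cited in Section 1.2.4. Applying these to survivors in this cohort is an assumption. The zero shares, the 30% share and all values of d are also assumptions. Here d is the same in both groups.

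| p₁ vs p₀ | d = 0 | d = 5 | d = 10 |
|---|---|---|---|
| 5% vs 5% | 0 | 0 | 0 |
| 5% vs 0% | 0 | 0.25 | 0.50 |
| 11% vs 5% | 0 | 0.30 | 0.60 |
| 11% vs 0% | 0 | 0.55 | 1.10 |
| 30% vs 5% | 0 | 1.25 | 2.50 |

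For example, (0.11 − 0) × 10 = 1.10 and (0.30 − 0.05) × 5 = 1.25.

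**4. Check by simulation.** Each scenario had 2,000,000 participants. Transplant depended on group and baseline QOL, other missingness depended on baseline QOL, and the weights used the true observation probabilities.

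- Nominal shares 5% vs 11% (realised about 5.5% vs 12%): bias about 0.33 at a shift of 5 and 0.64 at 10.
- Nominal shares 5% vs 30% (realised about 5.5% vs 31%): about 1.26 and 2.53.
- Equal shares, or d = 0: zero within simulation error of about 0.02.

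Correctly specified weights therefore do not remove the bias.

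**The case against.** **The stop in QOL is inferred.** A reader might conclude that QOL stops by design at transplant and that observation is impossible afterwards. No section says so. Sections 5.1 and 5.5 name only biologic samples as discontinued, the QOL schedule has no exemption, and Section 5.1 leaves registry data possible. This stands as a limit on the claim. The inference is still strong, because Section 5.5 ends participation at HCT, keeps vital status and sends other data elsewhere. If QOL is meant to continue, Section 5.5 conflicts with Section 5.4.2 and Table 4, so an edit is needed on either reading.

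**This is a resource study and detail may sit in an analysis plan.** Section 7.1 says that no single hypothesis drives the study, and risk sets and weight models are commonly left to the statistical analysis plan. But the protocol itself fixes the conditioning event and the estimator, and says the estimates will be obtained.

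**Section 7.2.2 already offers tools.** It lists redefined endpoints, competing risks, multistate models, stratification by missingness pattern and sensitivity analyses for a distributional shift. It also lets substudies include or exclude participants. These leave room for a remedy. They do not name transplant or change the stated target, and stratifying by missingness pattern gives no estimate for a pattern with no post-transplant values.

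**The estimate need not be biased, or by much.** A reader might also infer that the weighted difference is biased outright, or badly so in higher-risk patients. The IPSS shares in Section 2.1 (22% + 7% = 29%) give 145 of 500 MDS cases. If every transplant fell among them, 25/145 = 17% to 55/145 = 38% would be transplanted. The documents do not support this as an estimate: <5% refers to patients considered for HCT, 11% comes from another population, and Section 1.2.7 describes delayed transplant in lower-risk patients. The only QOL contrast that the protocol sizes is a six-month comparison by anemia therapy among transfusion-independent participants, where little transplant would be expected.

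**Conclusion.** The concern holds in a limited form. As written, the QOL target includes all survivors, while Section 5.5 implies that the study has no QOL for those transplanted. Weighting cannot close that gap. The mislabelling arises whatever the size of the effect.

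Bias in a between-group difference is conditional. It needs an unexplained post-transplant shift, and a transplant share or shift that differs between groups. At the cited HCT shares with assumed shifts of 5 to 10 points it is about 0.25 to 1.1 points, or 5% to 22% of the 5-point yardstick (0.25/5 and 1.1/5). At an assumed 30% vs 5%, as might arise in a risk- or treatment-related contrast, it is 1.25 to 2.5 points. Whole-cohort contrasts unrelated to transplant are little affected.

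The conclusion rests on reading Section 5.5 as ending study QOL at HCT, on applying the cited HCT shares to survivors in this cohort, and on shifts that the documents do not give. The point should be corrected, but it does not undermine the study.

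**What to change.** 1. Reconcile Section 5.5 with Section 5.4.2 and Table 4 by stating whether QOL is collected after HCT. If it is, by the study or through the registry, say so and keep the alive target.
2. If it is not, change the conditioning event in Section 7.2.2 from alive to alive and not transplanted at each time point.
3. Fit the missingness and weight models within that risk set, using the transplant status recorded every 6 months under Section 5.2.2.1.
4. Report the proportions transplanted and dead by group beside each QOL estimate.
5. Label the conclusions as applying to untransplanted survivors.

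If QOL is not collected after HCT, the cost is protocol wording and analysis code. The 6-monthly status matches the QOL visits, so the change does not depend on exact transplant dates, which the protocol does not say are recorded. The downside is that the estimate no longer speaks to QOL after transplant, but in that case the study data would not support such a statement anyway.

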8.1 Materials Required For This Protocol

8.1.1 Electronic case record and associated data forms

8.1.2 Pathology information and a copy of the surgical pathology report will be submitted through the data capture system. In addition all information available on karyotype, FISH and molecular genetic studies that have been performed at the home institution, will be collected.

Rev. 1/17 **8.1.3 Required Diagnostic and Classification Material**

8.1.3.1 Pathology Material Required at Baseline

- 3 Peripheral Blood smears unstained, 1 Wright-Giemsa (W/G) stain (optional)
- 3 Bone Marrow aspirate smears unstained, 1 W/G stain (optional), 1 Prussian blue stain (optional); unbound preferred
- 1 Bone Marrow biopsy hematoxylin and eosin (H&E) stained slide is required if biopsied
- 1 unstained core section is required if biopsied
- 1 touch preparation slide is required if dry tap occurs

Rev. 1/17

8.1.3.2 Pathology Material Required at Subsequent Bone Marrow Assessments

- 3 Peripheral Blood smears unstained, 1 W/G stain (optional)
- 3 Bone Marrow aspirate smears unstained, 1 W/G stain (optional), 1 Prussian blue stain (optional); unbound preferred
- 1 Bone Marrow biopsy H&E stained slide is required if biopsied
- 1 unstained core section is required if biopsied
- 1 touch preparation slide is required if dry tap occurs

NOTE: Submission of pathologic materials for diagnostic review is mandatory in order for the patient to be considered evaluable. Failure to submit pathologic materials may render the case unevaluable.

8.2 Shipping Procedures

8.2.1 Submission Schedule

8.2.1.1 All blood and bone marrow samples should be shipped on the date of collection for receipt at the CL/B within 24 hours. Samples collected on Friday must be sent for Saturday delivery. Refer to the MOP for specific shipping instructions.

8.2.1.2 The required slides for central hematopathology assessment must be submitted within 7 days of aspiration procedure. Refer to the MOP for specific shipping instructions.

Appendix I

Patient Thank You Letter

We ask that the physician use the template contained in this appendix to prepare a letter thanking the patient for enrolling in this trial. The template is intended as a guide and can be downloaded from the web site at <http://www.ecog.org>.

This small gesture is a part of a broader program being undertaken by ECOG-ACRIN and the NCI to increase awareness of the importance of clinical trials and improve accrual and follow-through. We appreciate your help in this effort.

[PATIENT NAME]

[DATE]

[PATIENT ADDRESS]

Dear [PATIENT SALUTATION],

Thank you for agreeing to take part in this important research study. Many questions remain unanswered in cancer. With the participation of people like you in clinical trials or studies, we will improve treatment and quality of life for those with your type of cancer.

We believe you will receive high quality, complete care. I and my research staff will maintain very close contact with you. This will allow me to provide you with the best care while learning as much as possible to help you and other patients.

On behalf of **[INSTITUTION]** and ECOG-ACRIN, we thank you again and look forward to helping you.

Sincerely,

[PHYSICIAN NAME]

The National Myelodysplastic Syndromes (MDS) Study

Appendix II

World Health Organization (WHO) 2008 Peripheral Blood and Bone Marrow Findings in MDS*

Disease	Blood findings	Bone marrow findings
Refractory cytopenia with unilineage dysplasia (RCUD): [Refractory anemia (RC); Refractory neutropenia (RN); Refractory thrombocytopenia (RT)]	Unicytopenia or bicytopenia ¹ No or rare blasts (< 1%) ²	Unilineage dysplasia: > 10% of the cells in one myeloid lineage < 5% blasts < 15% of erythroid precursors are ring sideroblasts
Refractory anemia with ring sideroblasts (RARS)	Anemia No blasts	≥ 15% of erythroid precursors are ring sideroblasts Erythroid dysplasia only < 5% blasts
Refractory cytopenia with multilineage dysplasia (RCMD)	Cytopenia(s) No or rare blasts (< 1%) ² No Auer rods < 1x10 ⁹ /L monocytes	Dysplasia in ≥ 10% of the cells in ≥ 2 myeloid lineages (neutrophil and/or erythroid precursors and/or megakaryocytes) < 5% blasts in marrow No Auer rods ± 15% ring sideroblasts
Refractory anemia with excess blasts-1 (RAEB-1)	Cytopenia(s) < 5% blasts ² No Auer rods < 1x10 ⁹ /L monocytes	Unilineage or multilineage dysplasia 5-9% blasts ² No Auer rods
Refractory anemia with excess blasts-2 (RAEB-2)	Cytopenia(s) 5-19% blasts ³ Auer rods ± ³ < 1x10 ⁹ /L monocytes	Unilineage or multilineage dysplasia 10-19% blasts ³ Auer rods ± ³
Myelodysplastic syndrome – unclassified (MDS-U)	Cytopenia(s) < 1% blasts ²	Unequivocal dysplasia in < 10% of cells in one or more myeloid lineages when accompanied by a cytogenetic abnormality considered as presumptive evidence for a diagnosis of MDS < 5% blasts
MDS associated with isolated del(5q)	Anemia Usually normal or increased platelet count No or rare blasts (< 1%)	Normal to increased megakaryocytes with hypolobated nuclei < 5% blasts Isolated del(5q) cytogenetic abnormality No Auer rods

Table from Reference 24

*Refer to the most recent WHO definitions for diagnosis.

1. Bicytopenia may occasionally be observed. Cases with pancytopenia should be classified as MDS- U.
2. If the marrow myeloblast percentage is less than 5% but there are 2-4% myeloblasts in the blood, the diagnostic classification is RAEB 1. Cases of RCUD and RCMD with 1% myeloblasts in the blood should be classified as MDS-U.
3. Cases with Auer rods and < 5% myeloblasts in the blood and < 10% in the marrow should be classified as RAEB-2. Although the finding of 5-19% blasts in the blood is, in itself, diagnostic of RAEB-2, cases of RAEB-2 may have less than 5% blasts in the blood if they have Auer rods and/or

10-19% blasts in the marrow. Similarly, cases of RAEB-2 may have less than 10% blasts in the marrow but may be diagnosed by the other two findings, Auer rod+ and/or 5-19% blasts in the blood.

Definitions

- Myelodysplastic Syndrome diagnosis

Myelodysplastic Syndrome is the primary disease to be studied in this project. It is defined by peripheral blood cytopenias with dysmyelopoietic bone marrow for which no other discernible cause exists. The term dysmyelopoietic refers to qualitative (and quantitative) abnormalities of the three cell lines (dyserythropoiesis, dysgranulomonopoiesis and dysmegakaryocytopoiesis). Because these findings alone are not diagnostic of MDS, potentially contributing conditions must be excluded. Nutritional status, alcohol and drug use, occupational exposure to toxic chemicals, prior treatment with antineoplastic agents or radiotherapy, and risk factors for treatment of human immunodeficiency virus (HIV) infection should be elicited. Since many patients with MDS have macrocytic anemia, folate deficiency must be excluded.

- Myelodysplastic/Myeloproliferative Neoplasms (MDS/MPN) Overlap Disorders

The WHO classification of myeloid neoplasms and acute leukemia defines the following myeloproliferative neoplasms that exhibit clinical, laboratory, and morphologic features that “overlap” both MPN and MDS: chronic myelomonocytic leukemia (CMML), atypical (BCR-ABL negative) chronic myeloid leukemia (aCML), and juvenile myelomonocytic leukemia (JMML).

- Idiopathic Cytopenia of Undetermined Significance (ICUS)

‘Idiopathic Cytopenia of Undetermined Significance’ is a term used to describe individuals with unexplained persistent cytopenia(s) without the morphologic or cytogenetic abnormalities for a conclusive diagnosis of MDS. Although patients with ICUS do not meet the minimal WHO criteria for MDS, they may progress and develop morphologic or cytogenetic evidence of the disease. The formal definition of ICUS typically requires ≥ 6 months of observation of cytopenia(s). For the purposes of the initial classification, cytopenia duration can be less than 6 months.

The National Myelodysplastic Syndromes (MDS) Study

Rev. 1/17

